**Validation of Machine Learning (ML) Models as Diagnostic Tools to
Predict Infection with SARS-CoV-2**

May 26, 2020

Machine learning models & Statistical analysis plan

Study Phases

The study will have multiple phases, each phase will consist of 14 days. This short time period reflects the urgent nature of the pandemic and declining infection rate in the UK, and a need to get validation data as soon as possible in an unpredictable environment.

Before the start of each phase (day 0), a set of machine learning models will be frozen and submitted for validation on data collected during this and subsequent phases. These will be numbered numerically according to the phase at which they were submitted; e.g. V1; V2 and so forth.

After the end of each phase (day 14), we will report on the performance of all models submitted for validation in this and previous phases, each on the complete dataset collected across all phases since that given model was submitted for validation.

Machine learning models improve with accumulation of data. Therefore it is necessary to continue data collection to train improved models which will be submitted for validation in later phases. Therefore 14-day phases will continue as long as tests are available and app users consent to joining the study.

Machine learning models

Four model types will be validated:

- a. Binary classifier to predict if infection is present/absent based on reported symptoms and phenotypic data. Variant tuned for high specificity, so with a bias towards false negative prediction
- b. Binary classifier variant tuned for high sensitivity, so with a bias towards false positive prediction
- c. Binary classifier variant tuned for a balance between specificity and sensitivity, so with a balance between false negative and false positive prediction
- d. Four-category classifier using the three classifiers a, b and c above to divide predicted chance of infection into a four point scale

For each model type, variants will be validated which produce outputs based on either symptoms reported during the first 2 days or during the first 3 days of symptoms.

These models will have been trained on a dataset of test results, reported symptoms and phenotypic data collected prior to the phase at which they are submitted for validation. The models will be frozen and described on GitHub at <https://github.com/zoe/covid-validation-study> before they are submitted for validation.

As described above, 14 day phases will continue whilst it is deemed of value to public health, and additional models may be submitted for validation before the start of each 14 day phase.

Statistical analysis plan

For each of the models, the primary validation metric will be the measured performance of the model's predictions compared to the 'gold standard' swab PCR tests on the entire unadjusted study population for the phases since they were submitted for validation.

In addition to models being frozen before they are submitted for validation, we will also record hashes of each day's data extracts when they are taken, to ensure integrity.

For each of the three binary classifiers, we will report sensitivity and specificity for each model on the entire unadjusted study population. We will estimate confidence intervals on these measures by bootstrapping from within the study population.

For the four-category classifier, we will report the measured percentage of the entire unadjusted study population falling in each pairing of a swab test result and one of the four categories as predicted by the model. We will estimate confidence intervals for these percentages by bootstrapping from within the study population.

In addition to these primary validation metrics on the entire unadjusted study population, we will also report performance for the same analyses on:

- Subgroups of the study population divided by age category (20-39, 40-59, 60-79), sex (male, female), ethnicity (white, black, asian), BMI category (underweight, normal, overweight, obese, severely obese), IMD (quintiles), healthcare worker (yes, no)
- A first rebalanced study population, where each participant has been weighted according the subgroups listed above (age category, sex, ethnicity, BMI category, IMD quintile, healthcare worker) such that the total weighting of each subgroup reflects its weighting within the UK adult population below 80 years old.
- A second rebalanced study population, skewed to overweight more vulnerable groups to reflect the highest regional levels of these vulnerabilities within the UK. Vulnerabilities to be considered are level of dependency (PRISMA7), history of heart disease, history of diabetes, history of lung disease and asthma.

Each of these analyses will be carried out only on those participants who have completed the corresponding phenotype fields.

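### The model input window is set by symptom day only and does not exclude symptom reports made after the participant learned the swab result, so accuracy may be biased if any result arrives before the window closes

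*SAP*

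**What the plan says.** Under the heading Machine learning models, the first classifier is described as a "Binary classifier to predict if infection is present/absent based on reported symptoms and phenotypic data". The other two binary classifiers are differently tuned variants of it, and the four-category classifier is built from all three. Each model type is validated in two versions, with outputs based on "symptoms reported during the first 2 days or during the first 3 days of symptoms". No other limit on the input window is given.

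Under Statistical analysis plan, the primary metric is "the measured performance of the model's predictions compared to the 'gold standard' swab PCR tests", taken "on the entire unadjusted study population for the phases since they were submitted for validation". For the binary classifiers, "we will report sensitivity and specificity for each model on the entire unadjusted study population".

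Two safeguards are named. On the models: "The models will be frozen and described on GitHub". On the data: "we will also record hashes of each day's data extracts when they are taken, to ensure integrity". The SAP does not say when the swab is taken relative to symptom onset, how long the result takes, or when and how the participant learns it.

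**The concern.** The index test is computed from what participants report about themselves. A participant who already knows the PCR result may report differently: more fully after a positive result, less or not at all after a negative one. Knowledge of the reference would then be part of the index test, and agreement between the two would overstate what the model can do before a result is known. That earlier moment is when a symptom-based predictor would be used.

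Nothing else in the SAP would reveal this:

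- Freezing fixes the algorithm and hashing fixes the files. Neither separates reports made before the result from reports made after it.
- Bootstrap intervals describe sampling error. As phases accumulate they narrow, while a bias of this kind stays.
- The subgroup and rebalanced analyses are defined by participant characteristics, not by the timing of reports.

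**Working it through.** The SAP states no target accuracy, sample size or timing figure, so there is no plan figure to reproduce. Two checks are possible.

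**1. When can a known result reach the input?**

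Count symptom onset as day 1. Let *s* be the symptom day of the swab and *t* the turnaround in days; both are assumptions. A report on day *d* can be influenced by the result only if *s + t* ≤ *d*, counting a same-day result as known. The last report day is *d* = 2 or *d* = 3, from the SAP.

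| s | t | s + t | 2-day variant exposed (≤ 2) | 3-day variant exposed (≤ 3) |
|---|---|---|---|---|
| 0 (day before onset) | 2 | 2 | yes | yes |
| 1 | 1 | 2 | yes | yes |
| 1 | 2 | 3 | no | yes |
| 2 | 1 | 3 | no | yes |
| 1 | 3 | 4 | no | no |
| 2 | 2 | 4 | no | no |
| 3 | 1 | 4 | no | no |

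Any pair with *s + t* ≤ 2 also has *s + t* ≤ 3. The 3-day variant can therefore never be less exposed than the 2-day variant. Its excess exposure may be nil.

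**2. How large could the effect be?**

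Let *f* be the share of participants who know the result inside the window. For sensitivity this means the share among PCR-positives, and for specificity the share among PCR-negatives. The same value is used for both here only for simplicity. Let *r* be the share of those otherwise misclassified whose reporting shifts enough to match the result. Then:

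- observed sensitivity = Se + f·r·(1 − Se)
- observed specificity = Sp + f·r·(1 − Sp)

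With true Se = 0.65 and Sp = 0.80 (assumed, as are all *f* and *r*):

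| f | r | f·r | Sensitivity | Specificity |
|---|---|---|---|---|
| 0 | any | 0 | 0.650 | 0.800 |
| 0.02 | 0.1 | 0.002 | 0.65 + 0.002 × 0.35 = 0.6507 | 0.80 + 0.002 × 0.20 = 0.8004 |
| 0.10 | 0.3 | 0.030 | 0.65 + 0.030 × 0.35 = 0.6605 | 0.80 + 0.030 × 0.20 = 0.8060 |
| 0.25 | 0.3 | 0.075 | 0.65 + 0.075 × 0.35 = 0.6763 | 0.80 + 0.075 × 0.20 = 0.8150 |
| 0.50 | 0.3 | 0.150 | 0.65 + 0.150 × 0.35 = 0.7025 | 0.80 + 0.150 × 0.20 = 0.8300 |

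Inflation runs from zero to 5.25 points in sensitivity and 3 points in specificity. If the assumed values are swapped (Se = 0.80, Sp = 0.65), the two maxima swap as well.

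A cruder calculation multiplies the share exposed by an assumed rise in correct classification. Shares of 5% to 20% with rises of 10 to 20 points give 0.05 × 10 = 0.5 up to 0.20 × 20 = 4 points, which is the same order of magnitude.

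**The case against.** The strongest reply is that swab timing and notification of results are study procedures, which belong in a protocol that is not shown. If the swab is taken late enough, or the result takes long enough, no report inside the window can be affected. The wording also helps: symptoms must be reported during the first 2 or 3 days, so later entries fall outside, and exposure needs a result within 2 or 3 days of onset. This stands as a limit on size. It does not dispose of the point, because the rule for what enters the model is set in this document and is silent on the result.

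A reader might go further and infer that post-result symptoms do feed the index test, that blinding is broken and that the 3-day variants are favoured. The SAP does not support this. It never says that any participant logs symptoms after a result; it only fails to exclude it. It plans no contrast between the 2-day and 3-day variants, although both will be reported and can be set side by side. Greater or equal exposure is not the same as a demonstrated advantage.

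The direction of bias is also an assumption. That people report in line with a known result is plausible, but nothing in the SAP establishes it. The sizes above multiply assumed quantities and include zero.

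**Conclusion.** The gap is real and conditional. The input rule lets reports made with knowledge of the swab result into the prediction if the result arrives before the window closes, and no stated safeguard or planned analysis would show it. The bias is most plausibly upward in both sensitivity and specificity, and the four-category table would be affected through the same inputs. Its size cannot be determined from the SAP: zero if no result returns inside the window, and up to about 5 points under the assumed ranges. The change is worth making because it is cheap. If no result returns early, it removes nobody and the reported count shows that.

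**What to change.** Add to the Statistical analysis plan section, in words such as:

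> For each model variant, sensitivity and specificity, or the four-category table, will also be reported for participants whose swab result was not known to them until after that variant's symptom window had closed. This will be shown beside the result for the full unadjusted population. The number of participants whose result was known before the window closed will be given by swab result and variant. If the two analyses differ, statements about predictive performance will rest on the pre-result analysis.

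The restriction should be applied to participants, not to individual reports. Truncating a participant's input at the result date would score a 3-day variant on perhaps one day of data, which is no longer the variant being validated. Under the rule above every input is a pre-result report and each variant is scored on its full defined window.

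The costs are a filter on log and result dates, a somewhat smaller sample per variant, and possibly slightly less favourable figures. The filter assumes that the date the result became known is in the extracts, which the SAP does not say. Participants with early results may also differ from the rest, so a gap between the two analyses could partly reflect who was left out and should be interpreted with the counts in view.

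### Do the SAP's two differently worded conditions for continuing the 14-day phases leave the end of validation undefined?

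*SAP*

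**What the plan says.** Under Study Phases, the SAP explains that models improve as data accumulate and draws the consequence: "Therefore 14-day phases will continue as long as tests are available and app users consent to joining the study". Continuation there depends on whether data can still be collected.

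At the end of Machine learning models, a second sentence reads: "As described above, 14 day phases will continue whilst it is deemed of value to public health". It then adds that further models may be submitted before each phase starts. Continuation here depends on a judgement of worth.

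Two other statements bear on the consequence. Study Phases sets the reporting rhythm: "After the end of each phase (day 14), we will report on the performance of all models submitted for validation", covering models from the current and previous phases, each on all data gathered since its submission. The Statistical analysis plan section defines the primary metric "on the entire unadjusted study population for the phases since they were submitted for validation".

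**The concern.** A sentence that claims to repeat an earlier rule ought to repeat it, and this one does not. Public-health value is not a condition under Study Phases. The stated reason there for going on is that "it is necessary to continue data collection to train improved models which will be submitted for validation in later phases". The nearest related remark, "This short time period reflects the urgent nature of the pandemic and declining infection rate in the UK", explains why a phase lasts 14 days, not when phases end.

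The setting makes the difference plausible in practice. With infections falling, tests and willing users could remain while a further phase is judged to add little. One sentence then says go on and the other permits stopping. Because the primary metric pools every phase since a model was submitted, the last phase decides which data enter that model's last cumulative result. Two readers could therefore expect the dataset to close at different points. Performance is also reported after every phase, so a discretionary decision to stop would be taken with results in view.

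**Working it through.** The SAP gives no sample size, event count or stopping boundary, so there is no figure of its own to reproduce. The check is a comparison of the two sentences.

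**Step 1: what the back-reference covers.** The sentence in Machine learning models has three elements.

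- Phases of 14 days that continue: described earlier, under Study Phases.
- Models submitted before each phase: described earlier ("Before the start of each phase (day 0), a set of machine learning models will be frozen and submitted for validation").
- Continuation conditional on public-health value: not described earlier.

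The back-reference holds for two elements and fails for one.

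**Step 2: where the two conditions diverge.**

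| Tests and consent available? | Judged of value? | Study Phases sentence | Machine learning models sentence |
|---|---|---|---|
| Yes | Yes | Continue | Continue |
| No | No | Stop | Stop |
| No | Yes | Stop | Continue, but no data can be collected |
| Yes | No | Continue | Stop |

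The third row settles itself. Only the fourth is a real difference, and it disappears if both conditions are required, which is the natural joint reading.

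**Step 3: what changes in the fourth row.** Suppose phase k is the last one judged worthwhile.

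- Under either sentence, the reports after phases 1 to k are identical: same frozen models, same comparison with swab PCR, same bootstrap intervals, same data.
- Under the Study Phases sentence there is also a report after phase k+1, on a larger cumulative dataset. It adds to the earlier reports and does not invalidate them.

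No estimand, metric, interval method or earlier report depends on which sentence governs.

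**Step 4: precision.** More phases give narrower intervals, whichever sentence is followed. For illustration, assume a sensitivity of 80% and 20 swab-positive participants per phase; neither figure is in the SAP. The approximate 95% half-width is 1.96 × √(0.8 × 0.2 / N).

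- 2 phases, N = 40: 1.96 × √(0.16/40) = 12.4 percentage points.
- 4 phases, N = 80: 1.96 × √(0.16/80) = 8.8 percentage points.

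The ratio is √2, as it must be when the data double. This shows the value of more data and does not measure harm from the wording. Whichever dataset is reported, its own interval shows the precision reached.

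**The case for a change.** The strongest case for an edit is that both sentences are in this SAP, so the mismatch cannot be put down to material left to a protocol. The document misdescribes its own text, does not say that both conditions must hold, and could be corrected in one sentence. All of that stands as a comment on drafting.

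The more serious form of the argument is optional stopping. If the judgement of value followed observed accuracy, the last cumulative estimate could be too favourable. Take an extreme assumed rule: true sensitivity 80%, at most 4 phases, stopping at the first cumulative estimate of 80% or more. Simulation (200,000 series) gives an upward bias in sensitivity of 3.7 points at 10 positives per phase, 1.8 at 50, 1.3 at 100 and 0.6 at 500. The SAP contains no such rule and nowhere links public-health value to observed accuracy. If continuation does not depend on results, this bias does not arise. Nor would joining the two conditions in one sentence remove the possibility, because the discretionary element would remain. The argument therefore gives no reason to reconcile the wording. Who judges public-health value is a matter of study governance, which a protocol commonly covers, so its absence here is not a fault.

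**Conclusion.** The observation about the text is right: the second sentence introduces a condition that the earlier section does not contain. It is a clerical slip in a cross-reference. The two conditions differ without contradicting each other, and an analyst would sensibly read them together as feasible and worthwhile.

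The effect on the definition or validity of any planned estimate is nil. The number of cumulative reports may differ, and the last one may be more or less precise, but each is sound for the data it covers. This rests on three features of the SAP: models are frozen before their phase, reporting is cumulative after every phase, and no test or sample size depends on an end date. It also assumes that continuation is not decided by the observed accuracy, and nothing in the SAP suggests that it is. Rewording would keep the same discretion and change no analysis, so no amendment is called for.

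### The only interval method is the bootstrap, which has zero width when no error is observed or a cell is empty and can under-cover when counts are sparse

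*SAP*

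**What the plan says.** In the SAP, section Statistical analysis plan, sensitivity and specificity of the three binary classifiers get this interval rule: "We will estimate confidence intervals on these measures by bootstrapping from within the study population". For the four-category classifier, which yields 2 swab results × 4 categories = 8 percentages, the rule is the same: "We will estimate confidence intervals for these percentages by bootstrapping from within the study population". No other interval method appears. There is no provision for zero errors, empty cells or small denominators, and no confidence level or bootstrap type.

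The section then adds that "we will also report performance for the same analyses on" subgroups and two reweighted populations. The interval sentence is not repeated there, but the natural reading is that it carries over. The subgroup levels number 3 (age) + 2 (sex) + 3 (ethnicity) + 5 (BMI) + 5 (IMD) + 2 (healthcare worker) = 20, or 20 × 8 = 160 subgroup cells for each four-category variant. These analyses lose further participants: "Each of these analyses will be carried out only on those participants who have completed the corresponding phenotype fields".

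**The concern.** Unweighted sensitivity, specificity and cell percentages are simple proportions. A resampling bootstrap learns the variability of a proportion only from events present in the sample. With none present it reports no uncertainty, and with few it tends to report too little.

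The design points towards such counts in several places:

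- Study Phases says of the 14-day phases: "This short time period reflects the urgent nature of the pandemic and declining infection rate in the UK".
- Models are scored "each on the complete dataset collected across all phases since that given model was submitted for validation", so a new version's first report rests on one phase.
- Under Machine learning models, classifier b is a "Binary classifier variant tuned for high sensitivity, so with a bias towards false positive prediction", so missed infections should be few. Classifier a is a "Variant tuned for high specificity, so with a bias towards false negative prediction", so false positives should be few. Each is therefore likely to have sparse errors on the measure it is built to do well on.
- If a, b and c act as nested cut-offs, the matching extreme cells of the four-category table would be sparse too.

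The bootstrap interval is the plan's only statement of uncertainty. No decision rule uses it, so what is at stake is a misleading report: 100% sensitivity with a 100%-100% interval claims certainty where there is least information.

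**Working it through.** **Inputs.** The SAP gives the method, the 8 cells, the 20 subgroup levels and the 14-day phase. It states no sample size, number of positives or interval width, so there is no figure of its own to reproduce. All counts below, and the 95% level, are assumptions.

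**Step 1: zero counts.** With x errors among n participants, each resample draws from the observed data. If x = 0, every resample has error rate 0, and both limits equal the estimate. This happens with probability (1 − p)^n, where p is the true error rate:

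- 5 positives, sensitivity 80%: 0.8^5 = 33%.
- 20 positives, sensitivity 90%: 0.9^20 = 12%.
- 50 positives, sensitivity 90%: 0.9^50 = 0.5%.

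By expected number of errors, the chance of a zero-width interval is 35-37% at 1, 11-13% at 2, 3-5% at 3 and under 1% at 5.

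With 10/10 detected, the bootstrap gives 100%-100%, Clopper-Pearson 69%-100% and Wilson 72%-100%. An empty cell with N = 100 gets 0%-0%, against an exact upper limit of 1 − 0.025^(1/100) = 3.6%.

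**Step 2: one coverage calculation in full.** With a fixed denominator and many resamples, the percentile limits are the 2.5% and 97.5% quantiles of Binomial(n, x/n), divided by n. Take 20 positives and a true miss rate of 10% (2 expected misses).

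- x = 0 gives 0%-0%, which excludes 10%.
- x = 1 gives 0%-15%, and x = 2 to 6 also include 10% (at x = 5 and 6 the lower limit is exactly 10%, counted as covering).
- x = 7 gives 15%-55%, which excludes 10%, as do larger x.

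Coverage = 1 − P(X = 0) − P(X ≥ 7) = 1 − 0.122 − 0.002 = 87.6%. Almost all of the shortfall comes from the zero-width case.

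**Step 3: the same sum over a grid.** n = 10-100 in steps of 5, then 150, 200, 300 and 500, with error or cell probability up to 0.5:

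| Expected errors or cell members | Percentile coverage, min-max | Mean |
|---|---|---|
| 0.5-1 | 39-65% | 52% |
| 1-2 | 63-89% | 77% |
| 2-3 | 86-96% | 91% |
| 3-4 | 80.5-96% | 87% |
| 4-5 | 91-98% | 93% |
| 5-6 | 88-98% | 91% |
| 6-10 | 88-97% | 94% |
| 10-20 | 91-97% | 94% |
| 20-30 | 92.5-97% | 95% |

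Coverage is saw-toothed, with dips just above 3 and just above 5 expected events. A basic bootstrap is worse in places: 61-89% at 2-3, 77-94% at 4-5 and 83-96% at 6-10. Resampling all participants, so that the number of positives varies, softens the dip near 3 but does not remove it (84-97% at 3-4, assuming 5% swab-positive).

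**Step 4: alternatives over 0.5-30 expected events.** Wilson covers 89.5-98% and Clopper-Pearson 95-99.7%. Keeping the bootstrap only when at least 10 errors and 10 non-errors are observed gives 89.5-99% with Wilson as the fallback and 92-99.7% with Clopper-Pearson.

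**Step 5: examples in both directions.** For specificity with 1800 negatives, percentile coverage is 82% at a true 99.9% (1.8 expected false positives) and 96% at 99% (18 expected). For sensitivity it is 96% with 50 positives at 90% and 96% with 100 positives at 80%.

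**Step 6: weighted estimates.** Simulation used 10-50 participants in the denominator and weights of 3:1 or 5:1. The effective size is (Σw)²/Σw².

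| Error rates across weight strata | Bootstrap | Wilson on effective size | Exact on effective size |
|---|---|---|---|
| Equal | 64-92% | 92-97% | 96-99% |
| Unequal | 47-93% | 90-98% | 94-99% |
| Unequal, 100 participants | 87-92% | 90-91% | 92-94% |

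**The case against.** The best counter-argument is about exposure. Sample size is commonly left to a protocol, which is not at hand, and the SAP does not show that counts will be sparse in the primary whole-population analysis. A falling national infection rate says little about the number of positives in the study. Tuning states a direction, not an error rate. Data accumulate for each model, so sparsity in a first report eases later. Subgroup intervals are inferred from wording, and subgroup results are secondary. No decision uses the interval, and a reader may recognise 100%-100% as degenerate.

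Most of this stands as a limit on how often the problem will be seen. It does not repair the method: a plan fixed before the counts are known has to say what happens when they are small.

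It is also fair that 10 is not a sharp boundary. Mean coverage is 94% on both sides of it, and the serious failures lie at about 4 expected events or fewer, with a smaller dip just above 5. Coverage at non-zero counts depends on the bootstrap type, and BCa and studentised forms were not evaluated. The zero-width result does not depend on type. Finally, the fallback for weighted populations is approximate and gains little at 100 participants.

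**Conclusion.** The concern holds. Zero width at zero counts is certain under the stated method, at any sample size. Under-coverage with sparse counts is confirmed for percentile and basic bootstraps at an assumed 95% level: severe below about 2 expected events, still as low as 80.5% (percentile) at 3-4, and milder and irregular up to about 10. Whole-population results with roughly 10 or more expected errors are little affected.

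How often the problem will arise cannot be determined from the SAP. The places to expect it are small subgroups, first reports after a single phase, and the error type each tuned classifier is meant to avoid. This should be fixed before the first report. It does not threaten the design, and the point estimates are unaffected.

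**What to change.** - **Unweighted proportions, overall and in subgroups.** As a minimum, report a Wilson or Clopper-Pearson interval instead of the bootstrap whenever fewer than 10 errors or fewer than 10 correct results (for cells, fewer than 10 members) are observed. Using one of these intervals for all unweighted proportions is simpler and avoids a switch.
- **Counts.** Print numerator and denominator beside each estimate.
- **Rebalanced populations.** Keep the bootstrap, but use a Wilson or exact interval on the effective sample size when the estimate is 0% or 100%, or when fewer than about 10 unweighted errors or cell members are observed. Compute that size among positives for sensitivity, among negatives for specificity and over everyone for cells.
- **Description.** State the confidence level, the bootstrap type, and whether resampling is within swab status or over all participants. This is a useful addition, but the main fix does not depend on it.

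The cost is a short SAP clause and a standard function call. Some intervals will be wider, and the weighted fallback is approximate: Wilson coverage was 90-92% in the worst simulated cases with unequal error rates.

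### Four-category classifier: joint swab-by-category percentages mix positivity with accuracy, and the conditional measures that separate them have no planned intervals (minor, cheap to improve)

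*SAP*

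**What the plan says.** In the SAP's section on statistical analysis, the three binary classifiers get measures conditional on the swab result: "we will report sensitivity and specificity for each model on the entire unadjusted study population". The four-category classifier gets a different kind of summary, a cross-tabulation of swab result by predicted level: "we will report the measured percentage of the entire unadjusted study population falling in each pairing of a swab test result". Its intervals attach to that summary alone: "We will estimate confidence intervals for these percentages by bootstrapping from within the study population". The SAP counts both among its primary validation metrics and repeats them in subgroups and in two rebalanced populations.

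Three other statements bear on how the cells behave:

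- **Changing positivity.** Under Study Phases, the 14-day phase length is explained thus: "This short time period reflects the urgent nature of the pandemic and declining infection rate in the UK".
- **Different windows.** Performance is reported for every model, "each on the complete dataset collected across all phases since that given model was submitted for validation", so successive versions are scored on different calendar windows.
- **Reweighting.** In the first rebalanced population, participants are weighted "such that the total weighting of each subgroup reflects its weighting within the UK adult population" under 80. Healthcare-worker status is one of the weighting factors.

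Under Machine learning models, item d says that the four-category classifier uses the three binary ones to "divide predicted chance of infection into a four point scale". The mapping from three classifiers to four levels is not given.

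**The concern.** A joint percentage answers how many people fall in a cell, not how well the model sorts infected from uninfected people. If positivity differs between two windows or populations, every cell can move while the classifier stays the same. A reader who compares one cell between versions, or between the unadjusted and a rebalanced population, may take a change in positivity for a change in accuracy.

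Item d presents the output as a graded chance of infection. The direct check of that claim is the observed proportion swab-positive in each category, with an interval. Neither this proportion nor any likelihood ratio is named as an output.

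**Working it through.** The SAP states no positivity, accuracy, sample size, weights or confidence level, so there is no figure of its own to reproduce. **Every input below is assumed, for illustration.** Intervals are 95%.

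**Inputs.** Categories run from 1 (lowest) to 4.

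| | Cat 1 | Cat 2 | Cat 3 | Cat 4 |
|---|---|---|---|---|
| P(category given positive) | 10% | 20% | 30% | 40% |
| P(category given negative) | 50% | 30% | 15% | 5% |
| Likelihood ratio (row 1 / row 2) | 0.20 | 0.67 | 2.0 | 8.0 |

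**Formulas**, with p the swab positivity:

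- positive cell = p × P(category given positive)
- negative cell = (1 − p) × P(category given negative)
- positivity in a category = positive cell / (positive cell + negative cell)

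**Step 1: versions.** V1 covers two equal phases. V2, the same classifier, covers only the second. The positive, category 3 cell is p × 0.30.

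| Positivity, phase 1 then 2 | V1 pooled p | V1 cell | V2 cell |
|---|---|---|---|
| 10%, 8% | 9% | 2.70% | 2.40% |
| 10%, 5% | 7.5% | 2.25% | 1.50% |
| 20%, 10% | 15% | 4.50% | 3.00% |

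Throughout, P(category 3 given positive) is 30% and the likelihood ratio is 2.0.

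**Step 2: rebalancing.** Suppose that healthcare workers are 40% of participants with 15% positivity, and the others have 6.67%. Overall positivity is 0.40 × 15% + 0.60 × 6.67% = 10%, so the cell is 3.00%. Weighted to 6% healthcare workers, positivity is 0.06 × 15% + 0.94 × 6.67% = 7.17%, and the cell is 7.17% × 0.30 = 2.15%. Accuracy has not changed.

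**Step 3: intervals not planned.** Take N = 1000 with 10% positive. Counts are 10/20/30/40 in positives and 450/270/135/45 in negatives. A percentile bootstrap of participants (20,000 resamples) gives:

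| | Estimate | 95% interval |
|---|---|---|
| P(category 2 given positive) | 20% | 12.5 to 28.1 |
| P(category 3 given positive) | 30% | 21.1 to 39.2 |
| Likelihood ratio, category 2 | 0.67 | 0.41 to 0.95 |
| Likelihood ratio, category 3 | 2.0 | 1.37 to 2.74 |
| Positivity, category 1 (10/460) | 2.2% | 0.9 to 3.6 |
| Positivity, category 2 (20/290) | 6.9% | 4.1 to 10.0 |
| Positivity, category 3 (30/165) | 18.2% | 12.5 to 24.2 |
| Positivity, category 4 (40/85) | 47.1% | 36.5 to 57.7 |

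For category 2 the likelihood-ratio interval is 0.31 to 1.08 at about N = 500 and 0.48 to 0.87 at N = 2000. Whether that level differs from no information can depend on an interval that is not planned.

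**Step 4: what a reader can recover.**

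- *From the binary classifiers, if nested.* Sensitivities of b, c and a are 90%, 70% and 40%; specificities are 50%, 80% and 95%. P(category 3 given positive) = sens(c) − sens(a) = 0.70 − 0.40 = 0.30. With 100 positives and the two estimates treated as independent, SE = √(0.21/100 + 0.24/100) = 0.0671. The interval is 16.9 to 43.1, or 26.3 points against 18.1 direct, about 45% wider.
- *From counts.* With N printed, the unweighted counts can be rebuilt. The simple binomial interval, 0.30 ± 1.96 × √(0.21/100), is 21.0 to 39.0, almost the direct one.
- *From weighted cells.* In the step 2 example, category 3 positivity is 13.4% (7.6 to 20.1; 12.5 points). Rescaling a binomial interval by the design effect implied by a planned cell interval gives 12.3 or 12.9 points. In a harder example, 30% of positives and 5% of negatives weigh 4.0 and the rest 0.67. Positivity is then 30.6% (19.1 to 41.8; 22.7 points). Rescaling gives 24.6 points from the positive cell (design effect 3.30) or 17.4 from the negative cell (1.65). Combining both cell intervals on the logit scale gives 21.6.

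**The case against.** The strongest reply is that nothing is lost. All eight cells are reported, and that is the complete cross-classification. Dividing each cell by its row or column total gives every conditional point estimate. This stands.

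Second, if the binary classifiers are nested cut-points of one score, their sensitivity and specificity are the accuracy of the four-point scale at all three cuts, including the middle one. They come with intervals, are repeated in every subgroup and rebalanced population, and do not mix in positivity. This also stands, subject to nesting, which is natural but not stated. A reader might infer that the four-point scale has no positivity-free accuracy in the plan, or cannot be validated; the document does not support that.

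Third, a reader might infer that the planned intervals are useless for conditional measures. Step 4 shows otherwise: with N the unweighted intervals follow directly, and the weighted ones can be approximated fairly well (21.6 points against 22.7 in the harder example). They remain approximations, and the SAP does not say that counts or N will be printed.

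Fourth, positivity per category itself depends on prevalence; in step 2 it falls from 18.2% to 13.4% with unchanged accuracy. That is right. It serves to check the scale in a given population, not to compare accuracy across populations.

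Finally, the SAP plans no test, threshold or cell-by-cell comparison of versions, so the harm needs a reader to misread a cell. This keeps the point minor. The restriction of subgroup and rebalanced analyses ("Each of these analyses will be carried out only on those participants who have completed the corresponding phenotype fields") is a separate matter, since it affects conditional measures equally; it is only a further reason to print N.

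**Conclusion.** The point holds as a minor, low-cost improvement. The primary metric for the four-category classifier mixes positivity with accuracy, in a study that expects infection to decline, scores versions on different windows and reweights its population. Single cells should not be compared as accuracy when positivity differs. The remaining gap is narrow: no direct, pre-specified interval for the conditional distribution in the two middle categories, for category likelihood ratios, or for observed positivity per category.

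The illustrative shifts (2.25% against 1.50%; 3.00% against 2.15%) and interval widths rest wholly on assumed positivity, category distributions, N and weights. Covering all three cuts through the binary classifiers rests on nesting.

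**What to change.** For the four-category classifier, amend the SAP as follows:

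- Report, as the accuracy measure, the category distribution within swab-positives and within swab-negatives, with the likelihood ratio for each category.
- Report the proportion swab-positive in each category as the check of the scale, and state that it varies with prevalence. State also that the conditional distributions are comparable between populations only if the spectrum of participants has not shifted.
- Take an interval for each measure from the bootstrap already planned, carrying the weights in the rebalanced analyses.
- Keep the joint table, with counts and N, as a descriptive display.

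The cost is a few lines of SAP wording, a re-tabulation of the same two-by-four data within each resample, and a slightly longer report after each phase. No new data are needed.
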